In addition to medical therapies, device therapies are available and have proven effectiveness, especially for improving HF symptoms and preventing sudden cardiac death (SCD). However, optimizing risk stratification and appropriately triaging individual patients to these invasive options to improve clinical outcomes remains a clinical challenge [Yancy et al. 2013] [Goldberger et al. 2011].

Present USA and European Union (EU) guidelines recommend implantation of an implantable cardioverter defibrillator device (ICD) in patients with left ventricular ejection fraction (LVEF) $\leq 35\%$ to reduce the risk of sudden death. Canadian guidelines [Bennett et al. 2017] further specify that additional risk assessment be performed in patients with LVEF values of 30% to 35% due to a lack of data supporting the use of prophylactic ICDs in this population.

Moreover, the recently-reported DANISH study has questioned the utility of prophylactic ICD therapy in patients with non-ischemic left ventricular dysfunction, possibly due to the lower risk of arrhythmic death with contemporary medical therapy. Further, only about half of all patients who meet the guideline-derived criteria actually have an ICD implanted reflecting the uncertainty of ICD benefit in patients with lesser degrees of left ventricular dysfunction. For example, in the first year after ICD implantation, as few as 5% of patients will actually experience a potentially fatal arrhythmia for which an ICD therapy is necessary [Moss et al. 2012]. Thus, the majority of patients who have an ICD implanted do not receive a survival benefit from it. These patients are not immune from the complications of device implantation and on-going care, including mechanical and infectious complications of the procedure, inappropriate device activation, device failure, and ultimately need for device replacement. Despite optimal therapy and device care, approximately 2% of patients with devices will die suddenly each year, and 3% will die from other cardiac causes, usually HF or myocardial infarction. Moreover, inappropriate shocks are associated with a higher incidence of all cause and cardiovascular death [Moss et al. 2012]. Ideally, only patients who will suffer a serious arrhythmia would have an ICD implanted. Yet, it is unlikely that this degree of risk stratification is attainable, given temporal changes in their underlying heart disease.

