10.2.6 Study Endpoints

Study endpoints will be documented and adjudicated according to the CEAC Charter.

A significant overlap between safety and efficacy events is expected. The study aims at comparing 2 prospective cohorts identifying a significant difference in patient outcomes. These outcomes will be composed of clinical events that usually conform to the definition of AEs and SAEs (i.e., death or prolonged hospitalisation). A set of specific criteria will be agreed upon by the CEAC defining efficacy events that will be used to identify those events that will require adjudication by the committee.

All AEs will be collected, analysed and (reported independently of their possible adjudication as an efficacy event), and according to Good Clinical Practice (GCP), legal and regulatory requirements.

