12.6.1 Efficacy Endpoints and Analyses (Secondary)

Key Secondary Endpoints

- A composite of the proportion of patients with hospitalisation or death related to major complications of device implantation (i.e., need for thoracotomy, pericardiocentesis, or vascular surgery) or complications of long-term device therapy (i.e., infection not leading to hospitalisation, lead and/or generator removal/replacement, inappropriate shocks, explantation). This endpoint will be analysed for superiority. These proportions will be compared between the patients with $H/M \geq 1.60$ in the AdreView™ group and the patients with $H/M \geq 1.60$ in the SoC group, using the Cochran-Mantel-Haenszel test stratified by enrolling centre, using a 2-sided alpha value of 0.050.

- Cardiac death. The occurrence of this event will be analysed in the primary efficacy population using a Cox proportional hazards model as was performed in the primary efficacy analysis (non-inferiority [NI], using an NI margin of 1.20).
- Rate of hospitalisation for cardiovascular cause. This rate will be compared between the AdreView™ and SoC groups using the Miettinen and Nurminen methodology [\[Miettinen and Nurminen 1985\]](#), (non-inferiority [NI], using an NI margin of 1.20).
- Rate of all-cause hospitalisation. This rate will be compared between the AdreView™ and SoC groups using the Miettinen and Nurminen methodology [\[Miettinen and Nurminen 1985\]](#), (NI, using an NI margin of 1.20).
- A composite of the occurrence of resuscitated life-threatening ventricular tachycardia, unstable ventricular tachy-arrhythmias, SCD and resuscitated cardiac arrest. The occurrence of this event will be analysed in the primary efficacy population using a Cox proportional hazards model as was performed in the primary efficacy analysis (non-inferiority, using an NI margin of 1.20).

Additional Secondary Endpoints

- Syncope. The occurrence of this event will be analysed in the primary efficacy population using a Cox proportional hazards model as was performed in the primary efficacy analysis (non-inferiority, using an NI margin of 1.20).

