Sample size estimates were also performed using plausible assumptions for the occurrence of the first key secondary endpoint, a composite of the proportion of patients with hospitalization or death related to major complications of device implantation (i.e., need for thoracotomy, pericardiocentesis, or vascular surgery) or complications of long-term device therapy (i.e., infection not leading to hospitalization, lead and/or generator removal/replacement, inappropriate shocks, explantation).

The following assumptions were made for these sample size estimates:

- Superiority analysis
- Alpha = 2-sided 0.05
- Power = 80% and 90%
- 1:1 randomisation to AdreView™ and SoC groups
- Proportion of SoC patients with $H/M \geq 1.60$ who have composite endpoint of harm (summarized above) from ICD implantation = 5%, 6%, 7%, 8%, 9%, or 10%
- Proportion of AdreView™ group patients with $H/M \geq 1.60$ who have composite endpoint of harm from ICD implantation = 0 (approximated by 0.0001).

Based on the above, the total sample size would range from 156 to 486 patients overall with a H/M ratio ≥ 1.6 . Thus, the sample size estimated for the primary efficacy endpoint was also adequate for the first key secondary endpoint (assuming 24% of patients in both the AdreView™ and SoC groups will have a H/M ratio ≥ 1.6 , approximately 500 patients overall with a H/M ratio ≥ 1.6 was expected).

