5.4.3 Secondary Efficacy Analyses

5.4.3.1 Key Secondary Endpoints Analyses

- A composite of the proportion of patients with hospitalisation or death related to major complications of device implantation (i.e., need for thoracotomy, pericardiocentesis, or vascular surgery) and a composite rate of complications of long-term device therapy (i.e., infection not leading to hospitalisation, lead and/or generator removal/replacement, inappropriate shocks, explantation). This endpoint will be analysed for superiority (odds ratio of AdreView™ vs SoC < 1.0). These proportions will be compared between the patients with H/M ≥ 1.60 in the AdreView™ group and the patients with H/M ≥ 1.60 in the SoC group, using the Cochran-Mantel-Haenszel (CMH) test stratified by country, using a 2-sided alpha value of 0.05.
- Cardiac death. The occurrence of this event will be analysed using a Cox proportional hazards model as described in the primary efficacy analysis (NI, using an NI margin of 1.20). Kaplan-Meier plot will be presented by method of treatment guidance. Patients who were alive or who had died from other than cardiovascular causes at the time of data base lock will be censored at the last known-alive date.
- Rate of hospitalisation for cardiovascular cause. The odds ratio of this rate will be compared between the AdreView™ and SoC groups using the CMH test stratified by country (NI, using an NI margin of 1.20).

- Rate of all-cause hospitalisation. The odds ratio of this rate will be compared between the AdreView™ and SoC groups using the CMH test stratified by country, (NI, using an NI margin of 1.20).
- A composite of the occurrence of resuscitated life-threatening ventricular tachycardia, unstable ventricular tachy-arrhythmias, SCD and resuscitated cardiac arrest. The first occurrence of these events will be analysed using a Cox proportional hazards model as described in the primary efficacy analysis (NI, using an NI margin of 1.20). Kaplan-Meier plot will be presented by the study arm. Patients who had not experienced any of the events at the time of data base lock will be censored at the last known-alive date.

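### The device-harm composite counts an outpatient device infection but not one that leads to hospitalisation, even if fatal, unless hardware is removed or replaced

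*SAP*

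**What the plan says.** Protocol 12.6.1 builds the composite from two parts.

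- **Part 1** is "hospitalisation or death related to major complications of device implantation (i.e., need for thoracotomy, pericardiocentesis, or vascular surgery").
- **Part 2** is "complications of long-term device therapy (i.e., infection not leading to hospitalisation, lead and/or generator removal/replacement, inappropriate shocks, explantation").

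SAP 5.4.3.1 repeats both lists, with the second reading "i.e., infection not leading to hospitalisation, lead and/or generator removal/replacement, inappropriate shocks, explantation". The same content stands in Protocol 10.1.2.1, 10.1.2.2 and 12.10 and in SAP 2.3, 3.1.2, 3.1.3 and 5.4.3.2.

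The composite is used twice. As the first key secondary endpoint it compares patients with H/M ≥1.6 between the arms, by proportions and a Cochran-Mantel-Haenszel test. As an additional secondary endpoint it compares all randomised patients with a Cox model.

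On event criteria, Protocol 10.2.6 says: "Study endpoints will be documented and adjudicated according to the CEAC Charter". That Charter is not among the documents.

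**The concern.** The composite is meant to measure the device harm that a patient avoids by not being implanted. Protocol Section 4 lists the harms in mind, "including mechanical and infectious complications of the procedure, inappropriate device activation, device failure, and ultimately need for device replacement", so infection is plainly one of them. Yet infection enters the definition only through Part 2, and there only when the patient is not admitted. The restriction makes sense if admitted infections were meant to be caught by Part 1, but Part 1 names three procedures and no infection.

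A more serious infection can therefore score nothing where a milder one scores an event. The reported rate of device harm would be too low, chiefly among patients who have devices.

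**Working it through.** **Step 1. Apply the two lists to concrete cases.** Each case assumes a device infection, none of the three Part 1 procedures, and no other qualifying event such as an inappropriate shock.

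| Course of the infection | Part 1 | Part 2 | Scores? |
|---|---|---|---|
| Treated as outpatient, device kept | no | yes, infection item | yes |
| Admitted, device kept | no | no, excluded by the restriction | **no** |
| Admitted, fatal before any removal | no | no, excluded by the restriction | **no** |
| Fatal with no admission | no | literally yes, but only as an infection without admission | yes, the death itself is not a component |
| Admitted, then lead or generator removed or replaced, or device explanted | no | yes, removal or explantation item | yes |

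The gap is rows two and three: admitted infections with no removal, replacement or explantation. At patient level the loss is confined to patients with no other component event.

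**Step 2. Look for text that fills the gap.** None of the sections listed above adds an infection that leads to admission or death. Deaths enter all-cause mortality and admissions enter all-cause hospitalisation, but neither endpoint isolates device harm.

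**Step 3. Direction.**

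- *H/M ≥1.6 comparison.* SoC patients are to receive an ICD and AdreView low-risk patients initially are not (Protocol 6.1, SAP 2.2). Missed events fall mainly in SoC. They do not fall only there, because low-risk patients may receive an ICD later (Protocol 9.4 and 9.5, SAP 2.2). The absolute harm avoided is understated, which works against superiority.
- *All-patient composite.* Protocol 12.10 assumes 24% with H/M ≥1.6, so 100% − 24% = 76% of the AdreView arm is also to be implanted. Missed events fall in both arms.
- *Both.* If the same share is missed in each arm, a ratio measure changes little. The loss shows in absolute rates and event counts.

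**Step 4. Check the plan's own figure.** Protocol 12.10 and SAP 2.3 give 156 to 486 patients, with "Alpha = 2-sided 0.05", power of 80% or 90%, "1:1 randomisation to AdreView™ and SoC groups", SoC harm p₁ = 5% to 10% and AdreView harm p₂ = 0.0001.

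Upper end (5%, 90% power), with p̄ = 0.02505 and d = 0.0499:

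- n = [1.960·√(2p̄(1−p̄)) + 1.282·√(p₁(1−p₁) + p₂(1−p₂))]² / d² = (0.4332 + 0.2796)² / 0.00249 ≈ 204
- Continuity-corrected: (n/4)·[1 + √(1 + 4/(n·d))]² = 51·(2.180)² ≈ 242.4, so 243 per arm and **486** in total, as stated.

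Lower end (10%, 80% power): the corrected formula gives 186 and the uncorrected 148. Exact power of the two-sided Fisher test gives 78 per arm (power 0.802), so **156**, as stated. Each end reproduces, by a different method.

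**Step 5. What these figures say about size.** The 5% to 10% is given for the composite as summarised in that section, that is, as written. At 0.24 × 2001 = 480, about 240 per arm, 5% is 0.05 × 240 = 12 counted SoC events. The number missed needs a rate of hospitalised device infection, which the documents do not give. For scale only, assume a share f of all SoC device-harm events is uncounted; the true total is then 12/(1 − f). With f = 10% it is 13.3 (1.3 missed, true rate 5.6%); with f = 30% it is 17.1 (5.1 missed, true rate 7.1%). Nothing in the documents supports any particular f.

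**The case against.** **The lists may not be closed.** The protocol uses the same abbreviation loosely elsewhere: in 10.1.5 before a list that ends with *etc.*, and in 10.2.6 before two examples of adverse events, although 10.2.8 has six seriousness criteria. This lowers certainty about Part 1. It does not supply the component: Part 2 still expressly leaves out admitted infections, and Part 1 concerns implantation, so a late infection fits it poorly even on a loose reading.

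**The Charter may settle it.** It may, and it cannot be checked. If it counts these events it departs from protocol and SAP, and the texts must be aligned. If it does not, the gap is real.

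**Severe infections often score anyway.** Correct where hardware is removed or replaced. A reader might infer that the composite keeps mild infections and drops severe ones altogether; the removal and explantation items show otherwise.

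**The formal consequence has gone.** A reader might also infer that the gap threatens the gate to the key-secondary hierarchy in Protocol 12.6. SAP 5.4.4 drops that hierarchy after early termination and makes all secondary analyses reference-only.

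**Power.** It is tempting to take 10% to 30% off the planned 5%, giving 4.5% to 3.5%. The 90%-power total would then rise from 486 to 542–702 (continuity-corrected), and power at 240 per arm would fall from 94% to 91%–83% (uncorrected). The documents do not support this. The share is unsupported, the 5% already refers to the composite as written, and 240 per arm presumes full enrolment. At a 10% harm rate the same exercise leaves power at about 99%.

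**Part 1 is a legitimate choice.** Restricting hospitalisation and death to major complications needing surgery or drainage can be defended. That other implant complications, such as pneumothorax, fall outside it is not an error.

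**Conclusion.** Wrong as written. In both documents a device infection that leads to admission, fatal or not, scores no event unless hardware is removed or replaced or the patient has another component event, while an outpatient infection does score. This follows from the text and needs no numerical assumption; the remaining uncertainty is the unseen Charter.

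In the H/M ≥1.6 comparison the effect is conservative: it understates the device harm avoided and does not manufacture a benefit. In the all-patient composite the loss is shared between arms, so the claim that nearly all missed events are in SoC should not be carried over. The size cannot be derived from the documents. No confirmatory claim depends on the endpoint now, but it will still be estimated and reported, and readers will take it as the rate of device harm.

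**What to change.** Replace the restricted infection item with *device-related infection, whether or not leading to hospitalisation or death* in Protocol 10.1.2.1, 10.1.2.2, 12.6.1 and 12.10, in SAP 2.3, 3.1.2, 3.1.3, 5.4.3.1 and 5.4.3.2, wherever the objectives and synopsis repeat it, and in the CEAC criteria. Leave Part 1 and its restriction to major complications unchanged.

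Before database lock, have the blinded CEAC re-check infection SAEs with a suspected relationship to ICD implantation. SAP Section 1 puts SAP sign-off before lock, so this can be done in sequence. If adjudication is already closed, report the corrected composite as a labelled sensitivity analysis beside the composite as now defined.

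No new data are needed: admission or death makes an infection an SAE (Protocol 10.2.8), and relationship to ICD implantation is recorded (SAP 5.5.2.4). The cost is some re-adjudication and a late definition change in a terminated trial whose sites know the allocation. The change adds events mainly in SoC in the H/M ≥1.6 comparison, so it tends to favour the sponsor's strategy. It must therefore be disclosed in the study report, as Protocol 12.13 requires for deviations, with both versions shown.

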2.3 Sample Size

The all-cause mortality rate that is expected in the study was estimated using the all-cause mortality rate observed in Study GE-122-016 at 36 months (internal report). It is assumed:

	Patients with $25\% \leq \text{LVEF} \leq 30\%$		Patients with $30\% \leq \text{LVEF} \leq 35\%$	
	%	Mortality Rate	%	Mortality Rate
H/M ratio <1.6	79%	20.25%	75%	15.14%
H/M ratio ≥ 1.6	21%	9.72%	25%	4.68%

In addition, the following observations or assumptions were taken: the ratio of patients with $25\% \leq \text{LVEF} \leq 30\%$ vs. $30\% \leq \text{LVEF} \leq 35\%$ is expected to be 1:4 to account for the prior enrollment of only patients with $30\% \leq \text{LVEF} \leq 35\%$; the hazard ratio of patients with ICD implantation vs. with usual care in the existing practice is 0.9 [Køber et al. 2016]. Referring to existing practice, only 15% of patients with $25\% \leq \text{LVEF} \leq 35\%$ currently receive ICD. Accordingly, the number of patients who currently do not receive ICD but who will receive it according to protocol and the number of patients who currently receive ICD and who will not receive it according to protocol have been calculated. In addition, the all-cause mortality rate of patients currently not receiving ICD but who will receive according to protocol (85% of patients with H/M ratio <1.6 in the AdreView™ group) has been corrected to take into account the 31% reduction in all-cause mortality observed at 20 months in the Multicentre Automatic Defibrillator Implant Trial (MADIT II) trial [Moss et al. 2012]. These assumptions led to a composite mortality rate of 11.34% in the AdreView™ group and 13.33% in the SoC group. The sample size was estimated with the hypothesis of not having a relative increase of mortality rate in excess of 20% in the AdreView™ group compared with the SoC group and with the following assumptions:

- Alpha = 0.025, 1-sided
- Statistical power = 80%
- 1:1 randomisation to AdreView™ and SoC groups
- $H_0: HR \geq HR_0$ vs. $H_1: HR < HR_0$. $HR_0 = 1.20$
- Assumed HR: 0.84
- Accrual time: 18 months
- The total study duration: 48 months
- AdreView™ group survival rate at 36 months: 0.887.

Based on the above assumptions, the required total number of events was 247, and the required total number of randomised patients was 2001. The planned study accrual was at least 2354 patients screened in order to randomise at least 2001 patients in the study.

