5.4.3.2 Additional Secondary Endpoints Analyses

- Syncope. The occurrence of this event will be analysed in the primary efficacy population using a Cox proportional hazards model as was performed in the primary efficacy analysis (NI, using an NI margin of 1.20). Patients who had not experienced syncope at the time of data base lock will be censored at the last known-alive date.
- Clinical and healthcare resource utilisation data collected in this study including ICD implantation, all hospitalisations, treatment of AEs, and AdreView™ administration will be used in an economic evaluation of study outcomes for relevant geographies. The clinical data may be summarised and compared between the AdreView™ and SoC groups. The healthcare resource utilization data will not be analysed due to early termination.
- A composite of the rate of hospitalisation and death related to major complications of device implantation (i.e., need for thoracotomy, pericardiocentesis, or vascular surgery) and a composite of the rate of complications of long-term device therapy (i.e., infection not leading to hospitalisation, lead and/or generator removal/replacement, inappropriate shocks, explantation). The occurrence of these events will be analysed using a Cox proportional hazards model as described in the primary efficacy analysis. These data will be analysed with a superiority analysis (HR of AdreView™ vs SoC < 1.0), using a 2-sided alpha value of 0.05. Kaplan-Meier plot will be presented by method of treatment guidance. Patients who had not experienced any of the events at the time of data base lock will be censored at the last known-alive date.
- The rate of ICD implantation and ICD explantation will be summarized for each study arm. In addition, the reasons of ICD implantation and ICD explantation will also be summarized. The odds ratio of the rate of ICD implantation and ICD explantation will be compared between the AdreView™ and SoC groups using the CMH test stratified by country.

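### Three secondary Kaplan-Meier plots censor deaths from other causes, so the absolute risks read from them are slightly too high

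*SAP*

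**What the plan says.** For cardiac death, SAP 5.4.3.1 sets the test as "The occurrence of this event will be analysed using a Cox proportional hazards model as described in the primary efficacy analysis", with a non-inferiority margin of 1.20. It adds "Kaplan-Meier plot will be presented by method of treatment guidance". The censoring rule is explicit: "Patients who were alive or who had died from other than cardiovascular causes at the time of data base lock will be censored". The date used is the one on which the patient was last known to be alive.

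The same section plans a Cox model and a Kaplan-Meier plot for the composite of resuscitated or unstable ventricular arrhythmia, sudden cardiac death and resuscitated cardiac arrest. SAP 5.4.3.2 plans both for the device-complication composite in the whole randomised arms. In both places the rule is "Patients who had not experienced any of the events at the time of data base lock will be censored", again at the last known-alive date. Death outside the endpoint is not mentioned, so a patient who dies of something else is censored by default.

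The key secondary device composite, restricted to patients with H/M ≥1.60, is handled differently. Proportions are compared "using the Cochran-Mantel-Haenszel (CMH) test stratified by country", and no curve is planned. Syncope (5.4.3.2) has the same censoring rule but no plot.

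Protocol 12.6.1 plans Cox models for these three endpoints and describes no curves. Neither document mentions competing risks or cumulative incidence. SAP 5.4.4 makes all secondary analyses reference only, because the sponsor ended the study early.

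**The concern.** Censoring in a Kaplan-Meier curve treats the censored patient as still able to have the event later, at the same rate as those who remain. That suits a patient whose follow-up simply ends. It does not suit a patient who has died of another cause, who can never have a cardiac death or a device complication. One minus Kaplan-Meier therefore estimates risk in a setting where the other deaths do not happen, and it lies above the proportion affected whenever such deaths occur. Here they are certain to occur, since all-cause mortality is the primary endpoint.

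What is at stake is the reading of absolute risk from the figures. The trial sets device harm avoided against deaths, and a reader may take both off these curves.

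**Working it through.** **Inputs from the documents.** SAP 2.3 gives a "composite mortality rate of 11.34% in the AdreView™ group and 13.33% in the SoC group". These are 36-month figures: the rates come from 36-month data, and the AdreView survival listed there is 0.887 at 36 months. SAP 2.3 also gives 5% to 10% device harm, but only for SoC patients with H/M ≥1.60.

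**Assumptions not in the documents.** Hazards are constant. Between 10% and 50% of deaths are non-cardiovascular. The 5% to 10% harm rate holds for a whole arm. Device complications and death are independent. All deaths compete with device complications; since device-related deaths count as events, this slightly enlarges the excess.

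**Plan's own figures first.** The documents state no value for the plotted risks, so the design figures are the nearest check.
- Events: 4 × (1.960 + 0.842)² / [ln(0.84/1.20)]² = 246.8, rounded up to the stated 247.
- Hazard ratio implied by the two mortality rates: ln(1 − 0.1134) / ln(1 − 0.1333) = 0.841, in line with the assumed 0.84.

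The mortality inputs are therefore being read as the plan reads them.

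**Formulas.** Let a be the monthly hazard of the event and b that of competing death.
- Plotted risk: 1 − KM = 1 − exp(−a·t)
- Cumulative incidence: CIF = a/(a+b) × [1 − exp(−(a+b)·t)]

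The SoC all-cause hazard is −ln(0.8667)/36 = 0.003974 per month.

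**Cardiac death at 36 months.** With a non-cardiovascular share f, a = (1−f) × the all-cause hazard and b = f × the all-cause hazard. For SoC with f = 0.3: 1 − KM = 1 − exp(−0.7 × 0.14306) = 9.53%, and CIF = 0.7 × 13.33% = 9.33%.

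| Arm | f | 1 − KM | CIF | Excess (points) |
|---|---|---|---|---|
| SoC | 0.1 | 12.08% | 12.00% | 0.08 |
| SoC | 0.3 | 9.53% | 9.33% | 0.20 |
| SoC | 0.5 | 6.90% | 6.66% | 0.24 |
| AdreView | 0.1 | 10.27% | 10.21% | 0.06 |
| AdreView | 0.3 | 8.08% | 7.94% | 0.14 |
| AdreView | 0.5 | 5.84% | 5.67% | 0.17 |

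A simulation of the SoC case with f = 0.3 (400,000 patients) gave 9.58% against 9.38%, the same gap.

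**Device complications at 36 months, SoC, b = all-cause hazard.** Set 1 − KM to 5% or 10%.
- At 10%: a·t = 0.10536 and b·t = 0.14306, so CIF = 0.10536/0.24842 × (1 − 0.90 × 0.8667) = 9.33%. The excess is 0.67 points, about 7% relative.
- At 5%: a·t = 0.05129, so CIF = 0.05129/0.19435 × (1 − 0.95 × 0.8667) = 4.66%. The excess is 0.34 points.

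**Early device harm.** Suppose half of the cumulative device hazard falls in the first 2 months. For the 10% case, a is 0.02634 per month to month 2 and 0.00155 after. The CIF is 5.11% up to month 2 plus 4.52% afterwards, which is 9.63%, an excess of 0.37 points. For the 5% case the CIF is 4.81%, an excess of 0.19 points.

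**Other horizons.** At 12 months the SoC excess is 0.01 to 0.03 points for cardiac death and 0.04 to 0.08 for device complications. At 48 months, the total duration in the sample-size assumptions, it would be 0.15 to 0.41 and 0.59 to 1.15 points.

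No figure can be given for the arrhythmia composite, because the documents state no event rate for it. The direction is the same.

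**The case against.** The strongest reply is that nothing decisive depends on these curves. The SAP asks for a plot and plans no risk estimate, risk difference or number needed to harm from it. Censoring other deaths in the Cox model gives a valid cause-specific hazard ratio. The device endpoint for which power was considered, in H/M ≥1.60, is a CMH comparison with no curve. All secondary results are reference only. The bias is also small beside sampling error: with about 1,000 patients per arm as planned, the standard error of a 9.3% risk is √(0.093 × 0.907/1000) = 0.9 points, against a 36-month bias of 0.2. It runs the same way in both arms, so the visual comparison moves little. All of this stands, and it limits the importance of the point.

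It does not make the curves right. A descriptive display should show the proportion of patients affected, and the correct estimator costs almost nothing.

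A reader might infer three stronger things, none of which the documents support.
- That the planned tests are invalid. They are not; the hazard ratios need only be named as cause-specific.
- That device harm in the H/M ≥1.60 comparison is overstated by Kaplan-Meier. No such plot is planned there.
- That the bias grows large over the study's expected duration of about six years. SAP 2.2 expects an average of only 2.75 to 3 years of follow-up per patient, and SAP 2.4 and 6 record early termination.

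**Conclusion.** The point holds as a minor presentation error in three plots: cardiac death, the arrhythmia/sudden-death composite and the whole-arm device composite. Other deaths are censored explicitly in the first and by implication in the other two, and the risks read from the curves are slightly too high.

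At the planned SoC mortality the 36-month excess is about 0.1 to 0.2 points for cardiac death and about 0.2 to 0.7 points for device complications; the lower end of the device range applies if harm falls early. These sizes rest on the assumptions listed in the working, above all the share of non-cardiovascular deaths and the use of a low-risk-subgroup harm rate for a whole arm. Shorter follow-up after early termination reduces them further. No planned test or trial conclusion changes.

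**What to change.** In SAP 5.4.3.1 (cardiac death; arrhythmia/sudden-death composite) and 5.4.3.2 (whole-arm device composite), replace the Kaplan-Meier plots with Aalen-Johansen cumulative incidence curves by study arm. The competing event is non-cardiovascular death for the cardiac death endpoint, and any death that is not itself an endpoint event for the two composites. Place it at the date of death, not at an earlier last known-alive date.

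Add a sentence that the Cox hazard ratios for these endpoints are cause-specific. Leave the Cox models, the CMH analyses and the Kaplan-Meier plot for all-cause mortality (SAP 5.4.2) as they are.

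The cost is a wording change and minor reprogramming of three figures. No new data should be needed: the date of death is required for the primary analysis, and SAP 3.1.3 has these endpoints adjudicated.
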